**Section 1: Project title****Section 2: Broad Subject**

Transfusion Medicine and Pulmonary Medicine

**Section 3: Duration**

The estimated total duration of the project is 4months.

**Section 4: Total Cost & FE Component: None****Section 5: Funding agency to which applying: None****Section 6: Project Category**

Investigator-Initiated Randomized Controlled Trial

**Section 8: Project summary**

Currently, no effective treatments are available for the COVID-19. Scientists and Researchers are working on many aspects of treatment options for the development of vaccination and medication to combat this life-threatening problem. Convalescent plasma from recovered COVID-19 patients contains antibodies against COVID-19 which may be beneficial to severely sick COVID-19 patients. We have recently concluded a pilot phase II open-label RCT on the efficacy of convalescent plasma in severe COVID 19 patients in which we have seen encouraging results. We plan to further study the efficacy and safety of convalescent plasma in COVID-19 severely sick patients through an RCT. We will collect up to 500 ml Convalescent Plasma from the COVID-19 recovered persons after 14 days of clinical recovery with two consecutive SARS CoV-2 negative tests by PCR at least 24 hours apart. This plasma will be tested and frozen and stored. On requisition it will be thawed and sent to the treating center. Two doses of 250 ml convalescent plasma each will be transfused on two consecutive days to patients who fit the eligibility criteria (Severely sick COVID-19 patients) and are randomized to the convalescent plasma group along with the standard of care and the other group will receive standard of care alone. Data will be collected to study the benefits and adverse events related to convalescent plasma transfusion.

[name] [name], MD  
Additional Professor - Transfusion Medicine  
Institute of Liver and Biliary Sciences  
[name]  
[name]

**Section 9: Subject Keywords****COVID-19, COVID-19 Convalescent Plasma, Donor Plasmapheresis, ARDS, Immunoglobulins, Antibodies****Section 10: State of knowledge**

The outbreak of severe acute respiratory syndrome due to COVID-19 (due to SARS-CoV-2 virus), which had originated in Wuhan, China, has become a pandemic involving more than 5million people across the globe. Currently, no specific drug therapy has been found useful with some benefits reported for remdisvir.

The virus causing COVID-19, SARS-CoV-2 is isolatable using VeroE6, Huh7, or human airway epithelial cells. Serological assays are needed for evaluation of the results of vaccine trials and the development of therapeutic antibodies. Among the four coronavirus structural proteins, the spike (S) and the nucleocapsid (N) are the main immunogens. Apart from antiviral treatment, virus-specific neutralizing antibody, which could accelerate virus clearance and prevent entry into target cells, serves as the main mechanism for the restriction and clearance of the viruses by the host. The convalescent plasma of the patients with these neutralizing antibodies can be used to treat patients with COVID-19. To date, no specific treatment has been proven to be effective for SARS-CoV-2 infection. The current evidence-based strategy relies on providing supportive care in mild cases and the need for mechanical ventilation and extracorporeal membrane oxygenation in severe cases. For over a century convalescent plasma has been used as prophylaxis or treatment of infectious diseases with variable success in different parts of the world

The experience of using convalescent plasma or immunoglobulins has been derived by its utility in improving the survival rate of patients with SARS wherein the patients who had no response to intravenous corticosteroids showed improvement. Lower mortality and shorter hospital stay were recorded for these patients. A study on 1775 patients by Cheng et al, the 80 patients who received convalescent plasma had a lower rate of mortality as compared to the overall mortality. They reported encouraging outcomes of the patients with the use of convalescent plasma in the 2003 SARS-CoV pandemic. In this study, they further found that 33 patients who received convalescent plasma transfusion within the two weeks of symptom presentation showed better outcomes. It has also been proven from previous studies that convalescent plasma can limit viral replication. Providing passive antibody therapy by convalescent plasma in COVID-19 could be one of the approaches towards disease mitigation in the absence of definitive therapy. Recovered donor convalescent plasma products demonstrate donor-related variations in antibody titers and specificities against specific infections.

**[name] [name], MD**  
Additional Professor - Transfusion Medicine  
Institute of Liver and Biliary Sciences  
[name]  
[name]

Convalescent plasma from recovered patients has shown improved survival in a recent study by Shen et al. on 5 critically ill patients with COVID-19. Improvements in Sequential Organ Failure Assessment (SOFA) Scores, PaO2 /FiO2, Acute Respiratory Distress Syndrome (ARDS) were seen along with a decrease in viral loads and an increase in protective antibody titres, although this intervention was not performed as a randomized clinical trial.

**Dose:** In recent reviews of studies on convalescent plasma therapy, the dose of CP has ranged from 200 ml to 600 ml in single or divided doses. This depends on the logistics of collection (The amount allowed in one donation as per the country's regulations). There is presently no consensus on the dose.

**Titer:** Neutralizing titre is difficult to perform as it requires a live virus culture and a BSL 3 facility. IgG/IgM titers can be done on ELISA (Most studies doing this method). Few studies have shown that IgG titre closely follows the neutralizing titre. The minimum titers vary from study to study (see Table 1)

#### Minimum Titre Requirements for Convalescent Plasma (ref-22-25)

Author	Country	Neutralizing antibody titer
Duan et al	China	>1:640
FDA recommendations	USA	>1:160 (1:80 acceptable)
ISBT Working party recommendations for convalescent plasma for LIC and MIC	-	1:160 (1:80 acceptable)
Shen et al	China	>1:40
Zhang et al	China	Not determined before transfusion
Joyner et al	USA	Not mentioned

The International Society of Blood Transfusion (ISBT) as well as the US FDA recommends a minimum titer of 80 (> 160 is preferable).

[name] [name], MD  
 Additional Professor - Transfusion Medicine  
 Institute of Liver and Biliary Sciences  
 [name]  
 [name]

## Risks

### Recipient Safety (ref:21)

In a recent report from Mayo Clinic, USA on 5000 convalescent plasma transfusions (CPT) in COVID-19 patients, 36 Serious Adverse Events (SAEs) were reported (< 1% of all transfusions). Of the 15 deaths reported (0.3% of all transfusions) four were judged to be related (possible: 3, definitely: 1) CPT. There were 21 non-death SAEs (see Table 2)

**Table 2: Serious Adverse Event (SAE) associated with convalescent plasma transfusion (n=5,000)**

Four hour mortality reports	Reported(n=36)	Related(n=25)	Estimated(95% CI)
Mortality	15	4	0.08% (0.03%, 0.21%)
Transfusion associated circulatory overload(TACO)	7	7	0.14% (0.07%, 0.29%)
Transfusion related acute lung injury(TRALI)	11	11	0.22% (0.12%, 0.39%)
Severe allergic transfusion reaction	3	3	0.06% (0.02%, 0.18%)
Seven Day reports	Reported		Estimated(95% CI)
Mortality	602		14.9% (13.8%, 16.0%)

**Donor Safety:** The convalescent plasma donation by Plasmapheresis was found to be a safe procedure in the RCT done at ILBS-MAMC. No adverse events were noted during 16 procedures done under this trial. No other studies reported any SAEs during donor plasmapheresis

### Section 11: Importance of the proposed project/ Justification for subject area:

COVID-19 is a major pandemic that has spread across all countries with a case-fatality rate varying from 1.2-10% or higher. Currently, there is no definitive therapy recommended for the management, and the results of convalescent plasma transfusion as a supportive therapy appear encouraging. The data from our pilot RCT is encouraging and therefore there is a need for a wider randomized controlled trial that could address the safety and efficacy of CP in the management of patients with severe COVID-19 using a larger sample size.

[name] [name], MD  
Additional Professor - Transfusion Medicine  
Institute of Liver and Biliary Sciences  
[name]  
[name]

If patients are counseled on recovery to donate convalescent plasma and this is frozen and sent to treatment centers, it may be used to transfuse severely sick patients and may improve outcomes.

### Section 12: Review of facilities and expertise available in the institution

The study will be carried out jointly at ILBS which has a fully functional Transfusion Medicine Department and facilities for collection of convalescent plasma and Delhi Govt. hospitals which are designated as COVID-19 treatment centers and are equipped with modern facilities for patient care and have the infrastructure for carrying out this study.

### Section 13: Study Design

#### Aim and Objectives

**Primary Objective:** To study the efficacy of convalescent plasma in severe COVID 19 patients in time to clinical improvement (Clinical improvement: Reduction of two points in ordinal scale or live discharge from the intensive care unit, whichever is earlier)

The six-point scale is as follows:

1. *death=6;*
2. *hospital admission for extracorporeal membrane oxygenation or mechanical ventilation=5;*
3. *hospital admission for non-invasive ventilation or high-flow oxygen therapy=4;*
4. *hospital admission for oxygen therapy (but not requiring high-flow or non-invasive ventilation)=3;*
5. *hospital admission but not requiring oxygen therapy=2;*
6. *discharged or having reached discharge criteria (defined as clinical recovery—ie, normalization of pyrexia, respiratory rate 94% on room air, and relief of cough, all maintained for at least 72 h)=1.*

#### Secondary Objectives:

1. The proportion of patients in each category according to the ordinal scale at 48 hours and day 7, 14, and 28 after randomization
2. Duration of oxygen therapy
3. Duration of hospital stay
4. The proportion of patients on mechanical ventilation at day 7.(after randomization)

[name] [name], MD  
Additional Professor - Transfusion Medicine  
Institute of Liver and Biliary Sciences  
[name]  
[name]

5. Mortality at day 7 and day 28 (after randomization)
6. Duration of Intensive Care Unit stay
7. Incidence of adverse effects in both groups
8. Presence of antibodies against SARS-CoV-2 in serum on days 0, 3, 7, 14, 21 & 28 after plasma administration, as long as the patient remains in the hospital.
9. Cytokines and acute phase reactants
10. To study the titers in COVID-19 convalescent plasma donors and correlate with duration of illness, the severity of symptoms, duration of hospital stay, drugs used in therapy, duration between recovery, and donation.

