**Study Design:**

An open label randomized controlled trial.

The study group will comprise of adult patients with severe COVID -19 as detailed above. Randomization will be done in the ratio of 3:1 in with 150 patients in the treatment arm and 50 patients in the control arm. Allocation concealment will be done by Sequentially Numbered Opaque Sealed Envelopes (SNOSE) method.

[name] [name], MD  
Additional Professor - Transfusion Medicine  
Institute of Liver and Biliary Sciences  
[name]  
[name]

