### Section 14: Inclusion and exclusion criteria for the admission of patients in the study

#### Inclusion criteria

Patients with severe COVID-19 (as described above) will be considered for randomization and will be transfused Convalescent Plasma within 3 days of symptom onset (Severe COVID-19)

**Severe COVID -19 defined** by WHO Interim Guidance and the Guideline of Diagnosis and Treatment of COVID-19 of National Health Commission of China (version 5.0) along with confirmation by real-time RT-PCR assay with severe disease i.e. meeting any 2 of the following criteria-

- Patients on ventilator (in last 24 hours)
- Respiratory distress, RR  $\geq$ 30 beats/min
- Oxygen saturation level less than 93% in resting state

[name] [name], MD  
Additional Professor - Transfusion Medicine  
Institute of Liver and Biliary Sciences  
[name]  
[name]

- Partial pressure of oxygen (PaO2)/oxygen concentration (FiO2) ≤ 300 mmHg
- Lung infiltrates > 50% within 24 to 48 hours

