#### **Patient Monitoring**

All included patients will be randomized to receive either 500 ml of convalescent plasma in two doses of 250 ml on two consecutive days along with the standard of care or standard of care alone

Clinical information of all enrolled patients including symptoms at presentation, time to presentation to the hospital, and development of pulmonary symptoms will be recorded. The details of comorbid diseases as measured by the Charlson index of co-morbidity and Acute Physiology and Chronic Health Evaluation II (APACHE II). Details of cross-sectional imaging, chest-x-ray, bacterial or fungal co-infections, and details of antibiotic treatment will be recorded. Development of complications including shock, acute kidney injury, acute coronary syndrome, myocarditis, acute respiratory distress syndrome, need for mechanical ventilation and nosocomial infection will be recorded. The use of high-flow oxygen, non-invasive, and invasive ventilation will follow standard guidelines and will be recorded. The details of antiviral treatment will be recorded for all enrolled patients.

[name] [name], MD  
Additional Professor - Transfusion Medicine  
Institute of Liver and Biliary Sciences  
[name]  
[name]

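### The day-7 ventilation outcome mixes failure to wean with new intubation and, as worded, counts an early death as not ventilated (minor)

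*Protocol*

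**What the plan says.** Item 4 of the Secondary Objectives is "The proportion of patients on mechanical ventilation at day 7.(after randomization". It is a status at a fixed time. It is neither limited to patients free of ventilation at randomisation nor split by that status.

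The Inclusion criteria (Section 14, repeated under Study Population) require "meeting any 2 of the following criteria", and the first of the five is "Patients on ventilator (in last 24 hours". The Exclusion criteria do not remove ventilated patients as such.

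On the six-point scale under Aim and Objectives, "hospital admission for extracorporeal membrane oxygenation or mechanical ventilation=5" is one level below death, which scores 6. Mortality at day 7 is a separate item (Secondary Objectives, item 5). Allocation is stated as "Randomization will be done in the ratio of 3:1 in with 150 patients in the treatment arm and 50 patients in the control arm". The list of methods under the Flow Chart heading names chi-square or Fisher's test for categorical variables.

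**The concern.** A patient can be on a ventilator at day 7 by two routes: ventilated at entry and not yet weaned, or intubated after randomisation. Both are unfavourable, but they answer different questions, and a single proportion cannot say which of them a difference, or its absence, reflects.

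Death is a second problem. A patient who dies on day 3 is not on a ventilator on day 7 and so leaves the numerator. Read literally, early deaths improve the result on an outcome where a lower figure is better. Item 4 is the only secondary objective devoted to ventilation, so readers will look to it for a claim about ventilation.

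**Working it through.** The protocol gives no expected ventilation rate, so there is no stated figure to reproduce. All rates below are assumptions used to show a range; only the arm sizes (150 and 50) and the 14.9% in step 5 come from the protocol.

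**1. Mixture.** Let b be the share ventilated at entry, s the chance that such a patient is still ventilated at day 7, and q the chance that any other patient is newly ventilated at day 7. The objective 4 proportion is b·s + (1 − b)·q. Take s = 0.70 in both arms, q = 0.20 in control and q = 0.10 under plasma (a true ratio of 0.50 for new ventilation).

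| b | Control | Plasma | Ratio |
|---|---|---|---|
| 10% | 0.07 + 0.18 = 0.25 | 0.07 + 0.09 = 0.16 | 0.64 |
| 20% | 0.14 + 0.16 = 0.30 | 0.14 + 0.08 = 0.22 | 0.73 |
| 30% | 0.21 + 0.14 = 0.35 | 0.21 + 0.07 = 0.28 | 0.80 |

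The shrinkage comes from assuming no effect on weaning. If plasma also halved s to 0.35, then at b = 20% plasma would be 0.07 + 0.08 = 0.15, and 0.15/0.30 = 0.50. Both parts halve, so the ratio is 0.50 at any b.

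**2. Share carried over from entry.** This is b·s / [b·s + (1 − b)·q] in the control arm. With q = 0.20 and s from 0.5 to 0.9 it is 22–33% at b = 10%, 45–60% at b = 25%, and 71–82% at b = 50%.

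**3. Power** (two-sided 5%, 50 v 150, q = 0.20, assumed relative risk 0.6, s from 0.5 to 0.9). With b = 0 it is 31%.

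| b | Effect on new ventilation only | Effect on both routes |
|---|---|---|
| 25% | 12–15% | 41–55% |
| 50% | 7–8% | 51–79% |

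Carry-over can lower or raise power, depending on where the effect lies.

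**4. Chance imbalance at entry.** At b = 20% the standard deviation of the between-arm difference in entry ventilation is √[0.2 × 0.8 × (1/150 + 1/50)] = 0.065. Multiplied by the control gap s − q = 0.50, this moves the between-arm day-7 difference by 3.3 points. The standard error of the 30% v 22% difference is √(0.30 × 0.70/50 + 0.22 × 0.78/150) = 0.073, or 7.3 points, and already includes that component. Its share of the variance is (3.3/7.3)² ≈ 0.20, so on these assumptions adjustment for entry status could remove about a fifth of the variance.

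**5. Death.** Suppose one arm has 20% ventilated and 10% dead at day 7, and the other 25% and 5%. Objective 4 reads 20% v 25% and favours the arm with twice the deaths; ventilated or dead is 30% in both. For scale only, the protocol's Table 2 gives 14.9% seven-day mortality in the cited series of 5,000 transfusions. At that rate 0.149 × 200 ≈ 30 patients here would be counted as not ventilated.

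**The case against.** The strongest reply is that day-7 prevalence is a legitimate outcome. Patients ventilated at entry can leave that state by weaning or by dying, so they carry information. Randomisation makes the arms comparable in expectation, and chance imbalance is already in the sampling error of the planned test. All of this stands, provided every randomised patient is in the denominator.

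It can also be said that item 1 reports every ordinal category at day 7 and item 5 reports day-7 mortality, so deaths are visible elsewhere. That is a partial answer: those figures show where patients are at day 7, not the state from which they started. Adjustment or stratified reporting may be in a statistical analysis plan that is not at hand, so its absence from the protocol is not held against it. What the protocol itself fixes is the state counted and, by its wording, the treatment of death.

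Two stronger readings are tempting. First, a reader might infer that the outcome largely re-counts the entry state. The ventilator criterion is optional: of the ten pairs of criteria that satisfy the entry rule, four include it, and pair counts are not patient shares. The share ventilated at entry is not given, and step 2 shows how strongly the answer depends on it. Second, a reader might extend the point to acute respiratory distress syndrome, because Patient Monitoring records "Development of complications including shock, acute kidney injury, acute coronary syndrome, myocarditis, acute respiratory distress syndrome, need for mechanical ventilation and nosocomial infection" while a PaO2/FiO2 limit is an entry criterion. That syndrome is a recorded complication, not a listed objective. The protocol does not define it by the oxygenation limit, and development already reads as new onset.

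**Conclusion.** The point holds as a minor one. Objective 4 combines two routes to ventilation and, as worded, treats death before day 7 as absence of ventilation. The arm comparison is not biased by this; what suffers is what can be concluded from it, and possibly its precision.

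The size cannot be fixed from the protocol. With 10% to 30% ventilated at entry, a halving confined to new ventilation would appear as a ratio of 0.64 to 0.80; if weaning improved equally, there would be no dilution. A reader might infer from the first set of figures that the outcome understates the effect of plasma. That rests wholly on assuming no effect on weaning, and the protocol does not say that objective 4 is meant to measure prevention of intubation.

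**What to change.** Keep the whole-population comparison and define it as ventilated or dead at day 7, with all randomised patients in the denominator, adjusted for or stratified by ventilation status at randomisation. In addition, report:

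- (a) among patients not ventilated at randomisation, new invasive ventilation or death by day 7;
- (b) among patients ventilated at randomisation, alive and off the ventilator at day 7, as a descriptive result only.

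Part (a) counts any event up to day 7 whereas the main figure is a status on day 7, so the parts will not add up exactly to the whole; the text should say so.

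The cost is wording. Ventilation use is already recorded under Patient Monitoring, and the primary outcome, a two-point fall on the scale, already needs each patient's starting level. The downside is small subgroups: at an assumed 20% ventilated at entry, (b) would hold about 0.2 × 50 = 10 controls and 0.2 × 150 = 30 plasma patients, and (a) about 40 and 120. For this reason (a) and (b) should supplement the whole-population outcome and not replace it.

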**For recipients:****1. Real-time PCR for SARS-CoV-2:**

Nasal swab samples will be taken prior to transfusion and tested for SARS-CoV-2 by real-time PCR method. The test should be positive for eligibility of the recipient along with clinical criteria for COVID-19.

2. Antibody titre: The serum of each recipient will be obtained and IgG antibody titre by enzyme-linked immune-sorbent assay (ELISA) or Rapid IgG antibody method will be tested one day prior to the convalescent plasma transfusion. Changes of IgG antibody titre before and after convalescent plasma transfusion in patients will be studied. The serum will be stored for neutralizing antibody titers by plaque reduction will be done subject to availability.

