## Flow Chart

- All variables shall be expressed in mean (SD) or median (range)
- Variables will be compared by Mann- Whitney U test
- For Categorical variables, we will use Chi-Square or Fisher's test
- Survival analysis will be done using Cox-proportional regression analysis

The actuarial probability of survival shall be calculated by Kaplan- Meier graph and compared by the log-rank test.

[name] [name], MD  
Additional Professor - Transfusion Medicine  
Institute of Liver and Biliary Sciences  
[name]  
[name]

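### Recipient antibody outcome is listed as presence in one place and as titre change in another, and the named tests cannot adjust for the pre-treatment titre

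*Protocol*

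**What the plan says.** Three places in the protocol bear on the recipient antibody outcome.

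- **Section 13, Secondary Objectives, item 8** lists "Presence of antibodies against SARS-CoV-2 in serum on days 0, 3, 7, 14, 21 & 28 after plasma administration", limited by the condition "as long as the patient remains in the hospital". The outcome is worded as yes/no, and the clock starts at plasma administration.
- **Antibody titre item for recipients** describes a quantitative measurement. An IgG titre by ELISA or "Rapid IgG antibody method will be tested one day prior to the convalescent plasma transfusion". It adds: "Changes of IgG antibody titre before and after convalescent plasma transfusion in patients will be studied".
- **Statistical methods (printed under Flow Chart)** give general rules only: "Variables will be compared by Mann- Whitney U test" and "For Categorical variables, we will use Chi-Square or Fisher's test". The one regression model named is for time-to-event data: "Survival analysis will be done using Cox-proportional regression analysis".

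The Study Design section sets 3:1 allocation, with 150 treated and 50 control patients. The protocol states no effect size, variance or power for any outcome, including this one.

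**The concern.** The objective and the methods text describe different outcomes. Read literally, objective 8 is categorical and goes to chi-square or Fisher at each sampling day. Read with the recipient-testing text, it is a titre or a change in titre and goes to Mann-Whitney. On neither reading can the named test use the pre-treatment titre as a covariate.

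The antibody data could help explain the primary result, whichever way it falls, by showing whether plasma raised recipients' antibody above the level that standard-care patients reach themselves. A presence comparison could miss a real difference in titre, particularly where most patients in both arms are already positive. With only 50 controls, precision is limited, and a baseline covariate that is already measured in recipients is a cheap way to recover some of it.

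**Working it through.** There is no protocol figure to reproduce, so this is an illustration.

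**Inputs from the protocol:** n = 150 treated and 50 control.

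**Assumptions, not in the protocol:** two-sided 5% test; normal log titres with SD 1; true shift d = 0.4 SD; 60%, 80% or 90% of controls positive; correlation rho between pre-treatment and follow-up log titre of 0.4 to 0.6; every patient sampled.

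**Standard error of a difference in means (SD units):** SE = sqrt(1/50 + 1/150) = 0.163.

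**1. Presence.** Treat positivity as a cut of the log titre, so that the treated proportion is pT = Phi(z(pC) + 0.4). Power = Phi[((pT - pC) - 1.96 x s0)/s1], where s0 is the pooled and s1 the unpooled standard error.

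| pC | pT | s0 | s1 | Power |
|---|---|---|---|---|
| 0.60 | 0.743 | 0.0743 | 0.0779 | 49% |
| 0.80 | 0.893 | 0.0550 | 0.0620 | 40% |
| 0.90 | 0.954 | 0.0387 | 0.0458 | 31% |

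**2. Raw follow-up titre.** Power = Phi(0.4/0.163 - 1.96) = Phi(0.49) = 69%.

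**3. Change in titre.** The SD becomes sqrt(2(1 - rho)).
- rho 0.4: SD 1.095, power Phi(2.236 - 1.96) = 61%.
- rho 0.6: SD 0.894, power Phi(2.739 - 1.96) = 78%.

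Below rho = 0.5 the change is less precise than the raw follow-up value.

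**4. ANCOVA on the pre-treatment titre.** The residual SD becomes sqrt(1 - rho^2).
- rho 0.4: SD 0.917, power Phi(2.673 - 1.96) = 76%.
- rho 0.6: SD 0.800, power Phi(3.062 - 1.96) = 86%.

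ANCOVA therefore gains about 15 points over change at rho 0.4 (76 - 61) and 8 points at rho 0.6 (86 - 78). Against raw titre it gains roughly 7 to 17 points.

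**Rank tests.** The Mann-Whitney test runs a few points below these normal-theory values. Simulation (1,500 trials per setting) gave 66% for raw titre and 56% and 73% for change at rho 0.4 and 0.6, against 75% and 85% for ANCOVA. All methods held their size at about 5%.

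**Sensitivity to the assumed shift, same formulas:**

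| Shift (SD) | Presence (90-60% of controls positive) | Raw titre | Change (rho 0.4-0.6) | ANCOVA (rho 0.4-0.6) |
|---|---|---|---|---|
| 0.3 | 21-31% | 45% | 39-54% | 52-63% |
| 0.4 | 31-49% | 69% | 61-78% | 76-86% |
| 0.6 | 52-80% | 96% | 92-98% | 98% to over 99% |

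**Chance imbalance.** The 95% range of the baseline difference in mean log titre is +/-1.96 x 0.163 = +/-0.32 SD. If half the patients are seropositive at entry, the range for the difference in seropositivity is +/-1.96 x sqrt(0.25 x (1/150 + 1/50)) = +/-16 percentage points.

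**The case against.** **The model is a matter for the SAP.** Choosing a covariate for the eighth of ten secondary objectives is commonly left to that document, which is not shown. This stands as far as the missing covariate alone is concerned. It does not dispose of the outcome itself, because the wording of objective 8 and the named tests are both in the protocol and fit poorly with the titre that the protocol also measures.

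**A reader might infer that the antibody outcome has been reduced to presence.** The documents do not support that. The recipient-testing text plans to study change in titre, and a change score already uses the baseline. The fault is that the two places disagree. Against the change-score reading, the gain from adjustment is about 8 to 15 points, not the larger gap from presence.

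**A reader might infer that the plasma itself guarantees positivity, so that presence tells nothing.** The protocol sets a minimum titre for donor plasma but says nothing about recipients' positivity after transfusion. The premise would also work against the low power figures: with 99% of treated patients positive, Fisher's test at 150:50 has about 80% to 100% power when 90% to 60% of controls are positive.

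**A reader might infer that the unadjusted comparison is biased by baseline imbalance.** Under randomisation the imbalance is due to chance and is covered by the test's error rate. It costs precision and is not a bias.

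**No between-arm antibody comparison is set out.** This stands. Objective 8 and the pre-transfusion titre are both tied to plasma administration, which controls never receive. The power figures apply only if the arms are compared, and day 0 must first be defined for controls.

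**Conclusion.** The point holds as a minor one. Objective 8 and the recipient-testing text name different antibody outcomes, and no test named for such variables can adjust for the pre-treatment titre. If the arms are compared, presence is clearly the weakest choice (about 31-49% power at the assumed 0.4 SD shift). The raw titre (69%) and the change (61-78%) fall short of a baseline-adjusted titre (76-86%) by smaller margins.

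The ordering of presence below raw titre, and of ANCOVA above both raw titre and change, holds across the shifts tried. The sizes rest wholly on the assumed shift, positivity, correlation, normality and complete sampling. In practice, sampling stops at discharge or death, so fewer patients contribute on later days and those who do are a selected group. Baseline adjustment does not cure that. The primary outcome is unaffected.

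**What to change.** - Reword objective 8 so that the outcome is the IgG titre, with seropositivity kept as a descriptive table.
- Count sampling days from randomisation in both arms, and state that controls are sampled on the same days. Specify that the day-0 sample is taken before any plasma; the present wording times day 0 from administration, while the recipient text places the titre one day earlier.
- Compare arms on log titre at each scheduled day, adjusted for day-0 log titre (ANCOVA, or a mixed model over days).
- Use one assay method per patient, since the protocol allows either ELISA or a rapid method, and state a rule for values below the assay limit.
- Report the number sampled by arm and day, and say plainly that sampling ends at discharge.
- Apply the same analysis to the cytokines and acute-phase reactants of objective 9 only if a day-0 value is taken.

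The cost is a rewording of objective 8 and a few lines in the statistical methods. If control samples on these days are not already planned, they are an added cost. A small downside is that the log-scale model depends on the rule for values below the assay limit, which a rank test tolerates more easily.
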